10 CRITERIA FOR EVALUATION AND ENDPOINT

Assessment of clinical outcomes:

Clinical outcomes will be assessed at various time points from the start of protocol treatment. Patients will be followed for a total of 2 years after enrollment.

A study subject that completes Cycle 1 of Tadium-223, EBRT, and at least 3 cycles of Radium-223 will be considered evaluable.

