10.1 Primary Endpoint – 15 month Hormone Free Survival

The primary objective is to determine the hormone-therapy-free survival time for men treated with sequential EBRT and Radium-223 and determine whether it is a 20% risk reduction over the institutional comparator of 100% use of systemic therapy by 15 months. The primary outcome is 15 months hormone-free survival. Patients will remain on study treatment for the duration defined by the calendar or for disease progression. Patients will be followed up to determine the start of ADT which will be used to measure the primary end point.

For the purposes of this study, progression will be measured after the completion of EBRT and the delivery of Cycle 2 of Radium-223 and defined as either:

Biochemical Progression:

- For those subjects whose PSA is greater than 20ng/ml at baseline who do not have any PSA decrease after starting therapy: biochemical progression will be defined as a 10% rise over the baseline.

- For those subjects whose PSA is greater than 20ng/ml at baseline, who demonstrate decrease in PSA after study treatment: if the PSA nadir remains > 20ng/ml, biochemical progression will be defined as a PSA rise greater than 10% of the PSA nadir. If the PSA nadir is < 20ng/ml, biochemical progression will be defined as a PSA rise greater than 10% of the PSA nadir.

-For those subjects whose PSA is less than 20ng/ml at baseline: biochemical progression will be defined as PSA >20ng/ml and 10%.

*Any PSA test that would meet a failure definition has to be validated through Huntsman Cancer Institute or a Veterans Affairs Hospital with a repeat PSA test no sooner than 5 days and no later than 14 days from the initial notification of the result demonstrating progression.

OR

Radiographic progression: Any new, progressing, or reappearing lesion on Bone Scan, CT/Scan, or MRI compared to the same scan performed previously. Radiographic Progression will be determined by Prostate Cancer Clinical Trials Working Group (PCWG2) and RECIST 1.1 as described below (section 10.1.1).

* Of note: For a patient to meet radiographic progression criterion for appearance of new bone lesion only, the patient must demonstrate appearance of new bone disease, as confirmed by the treating radiation oncologist, and also meet the biochemical progression definition set out above.

OR

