11 STATISTICAL CONSIDERATIONS

The primary objective is to determine the hormone-therapy-free survival time for men treated with concurrent EBRT and Radium-223 and determine whether 20% of subjects do not meet the progression endpoint and require ADT at 15 months. The primary outcome is 15 months hormone- (or other systemic) therapy-free survival. The null hypothesis is that 99% of subjects will start systemic therapy within 15 months. The alternative hypothesis is that 80% of subjects will start systemic therapy within 15 months. With 20 evaluable subjects there will be 93% power for this alternative hypothesis using an exact binomial test at the one-sided 0.05 significance level. The null hypothesis will be rejected if 2 or more out of 20 subjects are not placed on systemic therapy within one year.

One of the secondary endpoints is to determine the hormone-therapy-free survival time for men treated with concurrent EBRT and Radium-223 and determine whether it is a 30% risk reduction over the SWOG intermittent ADT historic cohort. This secondary hypothesis will be tested only if the primary null hypothesis is rejected. The outcome for

this secondary hypothesis is 15 month hormone- (or other systemic) therapy-free survival. In 2012 a SWOG cooperative group trial reported that 78% of subjects on intermittent androgen therapy had resumed ADT within 15 months, and this proportion will be used as a null hypothesis. With 20 evaluable subjects, and a null hypothesis that 78% or more of patients will start systemic therapy within 15 months there will be 80% power to detect an alternative hypothesis that 48% or fewer will start systemic therapy within 15 month using an exact binomial test at one-sided alpha =0.05 significance level.

Additional, secondary endpoints are time to first skeletal related event (SRE), overall survival, PSA doubling time, overall survival and toxicities. All secondary endpoints will be evaluated descriptively. Time to first SRE, OS, and PSA doubling time will be analyzed via Kaplan-Meier product limit methods and associated 95% confidence intervals. Toxicities will be tabulated using CTAE version 4.0. The number and proportion of subjects with toxicities will be reported.

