Exploratory endpoints are to evaluate if a commercially available cell-cycle progression gene assay (Myriad CCP) performed on the original prostate biopsy or surgical pathology specimen correlates with biochemical or clinical progression free survival in the study population.

Correlations with survival endpoints will be performed using exploratory Cox proportional hazards regression analysis.

Primary analysis and report planned at 15 months of follow up for all enrollees.

Health-related Quality of Life as scored by EPIC urinary, bowel, sexual, and hormonal domains, as well as PROMIS-29 questionnaires.

Medians, ranges, and quartiles will be computed for all health-related Quality of Life domains. Exploratory logrank tests will be used to relate domain scores to survival outcomes (hormone-free survival, time to first skeletal event, overall survival, and PSA doubling time).

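### Evaluability depends on treatment completed after baseline, both tests are sized on evaluable men, and the denominator is never stated; excluding early ADT starters would modestly flatter the ADT-free proportion and the SWOG comparison

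*Combined protocol and SAP*

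**What the plan says.** Section 10 sets the evaluability condition: "A study subject that completes Cycle 1 of Tadium-223, EBRT, and at least 3 cycles of Radium-223 will be considered evaluable". It does not say whether Cycle 1 is one of the three cycles, so three or four infusions may be needed.

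Section 11 uses the term in both power statements. For the primary test: "With 20 evaluable subjects there will be 93% power for this alternative hypothesis". For the SWOG comparison: "With 20 evaluable subjects, and a null hypothesis that 78% or more of patients will start systemic therapy within 15 months". The primary decision rule drops the qualifier: "The null hypothesis will be rejected if 2 or more out of 20 subjects are not placed on systemic therapy". The SWOG comparison is conditional: "This secondary hypothesis will be tested only if the primary null hypothesis is rejected".

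The Study Summary and Section 4.2 plan 20 men. No section gives a replacement rule, an allowance for non-evaluable men, or a statement on whether such men are excluded, replaced or counted as not free. The one reference to everyone enrolled concerns the timing of the report: "Primary analysis and report planned at 15 months of follow up for all enrollees".

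On follow-up, Section 10.1 says "Patients will be followed up to determine the start of ADT which will be used to measure the primary end point", and Section 7.4 keeps men who progress under follow-up after treatment stops.

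**The concern.** Whether a man is evaluable is settled after treatment begins and can depend on the outcome. The endpoint clock starts with study therapy (Section 1.1). Section 10.1 says "progression will be measured after the completion of EBRT and the delivery of Cycle 2 of Radium-223", which can be before the evaluability condition is met. Section 8.1.1 requires radium to stop on confirmed progression, and Section 7.3 does not allow ADT alongside study treatment. A man who starts ADT early may therefore never become evaluable, although he has had exactly the event that the primary endpoint counts.

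Leaving him out removes a failure from the denominator and no success from the numerator, so the ADT-free proportion rises. Men who stop for prolonged cytopenia or who withdraw while still ADT-free would push it the other way.

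At stake are the reported 15-month proportion and the SWOG comparison. With about 20 men, one exclusion can change the exact cut-off. Because the trial is open-label and single-arm, the denominator should be fixed before outcomes are known.

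**Working it through.** **Inputs from the plan (Section 11).** n=20; exact binomial, one-sided 0.05. Primary: 1% ADT-free under the null, 20% under the alternative, reject at 2 or more. SWOG: 22% free under the null (100−78), 52% under the alternative (100−48). The SWOG cut-off is not stated; it is taken as the smallest count with exact p at or below 0.05.

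**Assumption.** The documents give no early-ADT rate. Let f be the share of treated men who start ADT before becoming evaluable; f=5% to 10% is the main case and 30% an upper bound.

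**1. The plan's own figures.**
- Primary: P(X≥2 | 20, 0.01)=0.017; P(X≥2 | 20, 0.20)=0.931. The stated 93% reproduces.
- SWOG: P(X≥8 | 20, 0.22)=0.054 is too large and P(X≥9 | 20, 0.22)=0.019, so the cut-off is 9. P(X≥9 | 20, 0.52)=0.802. The stated 80% reproduces.

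**2. Proportion if early starters are excluded.** The rate among evaluable men is p/(1−f). For p=0.20: 0.20/0.95=0.211 and 0.20/0.90=0.222. At f=30%, 0.20/0.70=0.286.

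**3. SWOG type I error (true rate 22% free; 1.9% with all 20 men).**
- With replacement to 20 evaluable: P(X≥9 | 20, 0.22/(1−f)).
- Without replacement: n is Binomial(20, 1−f), the cut-off is reset for each n (9 at n=20, 8 at n=17 to 19, 7 at n=14 to 16), and the result is averaged over n.
- Random loss: as the previous line, but with the rate held at 22%. This isolates the effect of the smaller n.

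| f | With replacement | Without replacement | Random loss |
|---|---|---|---|
| 5% | 2.6% | 3.8% | 2.9% |
| 10% | 3.6% | 5.3% | 3.0% |
| 30% | 14.4% | 15.6% | 3.1% |

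At f=5% without replacement, the rise is 3.8−1.9=1.9 points, of which 2.9−1.9=1.0, about half, is the smaller n.

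**4. Primary type I error.** Without replacement it stays at 1.7%: excluding early starters adds no successes, and the exact cut-off stays at 2 for n=6 to 30. With replacement, P(X≥2 | 20, 0.01/(1−f)) is 1.9% to 2.1% at f=5% to 10% and 3.3% at f=30%.

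**5. Offsetting exclusions.** With 10% early starters, plus 5% lost to toxicity or withdrawal of whom half are ADT-free, a true 20% reads as (0.20−0.025)/0.85=0.206. SWOG type I error is 2.4% with replacement and 3.8% without.

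**6. One man.** P(X≥8 | 20, 0.22)=0.054 (not rejected); P(X≥8 | 19, 0.22)=0.040 (rejected).

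**7. How often the two denominators disagree on SWOG** (no replacement, cut-off reset). They disagree when the ADT-free count reaches the reset cut-off but not 9.

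| True ADT-free rate | f=5% | f=10% |
|---|---|---|
| 20% | 1.2% | 2.2% |
| 22% | 2.0% | 3.4% |
| 40% | 12% | 19% |
| 52% | 8% | 11% |

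**8. Chance that the issue arises.** If 5% are non-evaluable, all 20 men are evaluable with probability 0.95^20=0.36; at 10%, 0.90^20=0.12.

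**The case against.** The best defence is that the text leans towards all 20 men: 20 are planned, the decision rule is out of 20, all enrollees are mentioned, and nothing provides for replacement. That is a fair reading, but the sentence before the rule says evaluable, and the all-enrollees sentence fixes only when the report is made. Neither settles the denominator.

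Second, there may be little room for early exclusion. Progression counts only after EBRT and Cycle 2, a qualifying PSA must be repeated 5 to 14 days later, treatment may continue meanwhile (Sections 8.1.1 and 10.1), and the first required bone scan falls between Cycles 3 and 4 (Section 9, note 6). If Cycle 1 is one of the three cycles, few protocol-defined progressions can precede evaluability. This stands, and is why 5% to 10% is the main case. If the three cycles are additional to Cycle 1, there is more room.

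Third, the SWOG comparison is secondary, and a later sentence in Section 11 calls all secondary endpoints descriptive. Yet it has a null, an alpha, a power and a testing condition, so it functions as a test. The 8-of-19 example also owes something to discreteness: the cut-off falls from 9 to 8 whoever is missing. That too stands.

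A reader might infer that the primary conclusion is unsafe, or that the plan excludes early failures. The documents support neither: the primary rule is robust, and no section directs any exclusion.

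**Conclusion.** The concern holds as a modest, conditional one that should be fixed. The plan defines evaluability by treatment completed after baseline, sizes both tests on it, enrols exactly that number, and leaves the denominator open. Using evaluable men could bias the reported proportion and the SWOG comparison, most plausibly upward.

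At the assumed 5% to 10% early starters, the proportion is overstated by about one to two points. SWOG type I error stays near or below 5% (at most 5.3%). SWOG verdicts differ in about 1% to 3% of trials at 20% to 22% ADT-free, 8% to 11% at the plan's 52%, and up to 19% at intermediate rates that the plan does not name. The primary decision is essentially safe.

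Type I error of 14% to 16% needs 30% early starters, for which the documents offer no support. Replacement to 20 evaluable men and a reset cut-off are likewise assumptions about how the plan might be carried out, not provisions in it.

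**What to change.** In Sections 10 and 11:

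- State that both tests use all men who receive any study treatment.
- Count any start of ADT or other systemic therapy before 15 months as not free, whatever number of cycles was completed.
- State the SWOG cut-off: 9 or more ADT-free of 20.
- Keep the evaluable set as a supportive analysis only, and state whether Cycle 1 counts among the three cycles.
- State whether the 20% and 52% alternatives describe all treated men or only evaluable men.

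If they describe all treated men, power stays 93% and 80%. If they describe only evaluable men and the rest count as not free, restate power as P(X≥2 | 20, 0.20(1−q)) and P(X≥9 | 20, 0.52(1−q)), where q is the non-evaluable share: 92% and 73% at q=5%, 90% and 65% at q=10%.

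The cost is wording and a power statement. No new data are needed, since Sections 7.4 and 10.1 already keep progressors under follow-up and track the start of ADT. The change itself needs no additional enrolment. The downside is that the estimate may be slightly less favourable.

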10.1 Primary Endpoint – 15 month Hormone Free Survival

The primary objective is to determine the hormone-therapy-free survival time for men treated with sequential EBRT and Radium-223 and determine whether it is a 20% risk reduction over the institutional comparator of 100% use of systemic therapy by 15 months. The primary outcome is 15 months hormone-free survival. Patients will remain on study treatment for the duration defined by the calendar or for disease progression. Patients will be followed up to determine the start of ADT which will be used to measure the primary end point.

For the purposes of this study, progression will be measured after the completion of EBRT and the delivery of Cycle 2 of Radium-223 and defined as either:

Biochemical Progression:

- For those subjects whose PSA is greater than 20ng/ml at baseline who do not have any PSA decrease after starting therapy: biochemical progression will be defined as a 10% rise over the baseline.

- For those subjects whose PSA is greater than 20ng/ml at baseline, who demonstrate decrease in PSA after study treatment: if the PSA nadir remains > 20ng/ml, biochemical progression will be defined as a PSA rise greater than 10% of the PSA nadir. If the PSA nadir is < 20ng/ml, biochemical progression will be defined as a PSA rise greater than 10% of the PSA nadir.

-For those subjects whose PSA is less than 20ng/ml at baseline: biochemical progression will be defined as PSA >20ng/ml and 10%.

*Any PSA test that would meet a failure definition has to be validated through Huntsman Cancer Institute or a Veterans Affairs Hospital with a repeat PSA test no sooner than 5 days and no later than 14 days from the initial notification of the result demonstrating progression.

OR

Radiographic progression: Any new, progressing, or reappearing lesion on Bone Scan, CT/Scan, or MRI compared to the same scan performed previously. Radiographic Progression will be determined by Prostate Cancer Clinical Trials Working Group (PCWG2) and RECIST 1.1 as described below (section 10.1.1).

* Of note: For a patient to meet radiographic progression criterion for appearance of new bone lesion only, the patient must demonstrate appearance of new bone disease, as confirmed by the treating radiation oncologist, and also meet the biochemical progression definition set out above.

OR

Clinical Progression: the development of any skeletal related event defined as: time to any EBRT not required as a study procedure, time to first pathological bone fracture, time to spinal cord compression, or time to surgical intervention.

RECIST 1.1 and PCG 2 Assessments:

The following definitions and criteria for RECIST 1.1 and PCWG2 should be used for the baseline evaluations of existing disease and for the ongoing evaluation of tumor responses.

Measurable lesions - lesions that can be accurately measured in at least one dimension with longest diameter (LD) ≥ 10 mm using CT, MRI, or caliper measurements or ≥ 20 mm with x-ray.

Non-measurable lesions - all other lesions including small lesions (LD < 10 mm with CT, MRI, or caliper measurements or < 20 mm with x-ray).

Documentation of “Target” and “Non-Target” Lesions

- All measurable lesions up to a maximum of two lesions per organ and five lesions in total, representative of all involved organs should be identified as ***target lesions*** and recorded and measured at baseline.
- Target lesions should be selected on the basis of their size (lesions with the longest diameter) and their suitability for accurate repeated measurements (either by imaging techniques or clinical assessments).
- A sum of the LD for *all target lesions* will be calculated and reported as the baseline sum LD. The baseline sum LD will be used as the reference by which to characterize the objective tumor response.
- All other lesions (or sites of disease) should be identified as ***non-target lesions*** and should also be recorded at baseline. Measurements of these lesions are not required, but the presence or absence of each should be noted throughout follow-up.

RECIST Response Criteria

Evaluation of target lesions	
Complete Response (CR)	Disappearance of all target lesions (Must persist for a minimum of four weeks)
Partial Response (PR)	At least a 30% decrease in the sum of the LD of target lesions, taking as reference the baseline sum LD (Must persist for a minimum of four weeks)
Progressive Disease (PD)	At least a 20% increase in the sum of the LD of target lesions, taking as reference the smallest sum LD recorded since the treatment started or the appearance of one or more new lesions
Stable Disease (SD)	Neither sufficient shrinkage to qualify for PR nor sufficient increase to qualify for PD, taking as reference the smallest sum LD since the treatment started

Evaluation of non-target lesions	
Complete Response (CR)	Disappearance of all non-target lesions
Stable Disease (SD)	Persistence of one or more non-target lesion(s)
Progressive Disease (PD)	Appearance of one or more new lesions and/or unequivocal progression of existing non-target lesions

RECIST Evaluation of Overall Response

The best overall response is the best response observed until progression/recurrence and is determined as indicated in the table below:

Target Lesions	Non-Target Lesions	Evaluation of New Lesions	Overall Response
CR	CR	No	CR
CR	SD	No	PR
PR	Non-PD	No	PR
SD	Non-PD	No	SD
PD	Any	Yes or No	PD
Any	PD	Yes or No	PD
Any	Any	Yes	PD

Radionuclide Bone Scan Assessment

Bone scan lesions should be enumerated at baseline. Questionable lesions, e.g., sites of previous fracture, may require confirmation by CT or MRI.

Post-baseline Assessments and Definition of Progression of Bone Metastases

Disease Based on Radionuclide Bone Scan

Bone scan lesions should be assessed and enumerated at each follow-up assessment.

Progression on bone scan is defined as 2 or more new lesions on radionuclide bone scans. Should 2 or more new bone lesions be evident at the first assessment on treatment (end of cycle 3), 2 or more additional new lesions must be evident on a confirmatory assessment at least 6 weeks later (and no sooner than end of cycle 6). This confirmation is not required when 2 or more new lesions (compared to baseline or to the end of cycle 3 assessment) first appear after the first follow-up assessment, i.e., at end of cycle 6 or thereafter.

Should new bone lesions be documented at end of cycle 3 but not confirmed at end of cycle 6, then end of cycle 3 scan becomes the new baseline and 2 or more new lesions at subsequent assessments relative to end of cycle 3 defines bone scan progression.

Stable disease (SD) on bone scan stable disease is defined as the absence of progression. Bone scan lesions are considered non-evaluable under RECIST, and thus there can be no partial response. Complete response is very rare. Thus, almost all bone scans will be rated as NE (no lesions present), SD, or PD.

Overall Response Assessment

The following table summarizes the overall response status calculation at each time point for patients who have either RECIST 1.1 evaluable soft tissue lesions and/or radionuclide bone scan lesions. Note that CR can only occur if there are RECIST 1.1-evaluable lesions and no bone lesions based on radionuclide bone scan. PR can occur if patients have CR or PR based on soft tissue evaluation and bone scan lesions that are stable.

Overall Assessment Time Point Response

PCWG2 Target/Nontarget soft tissue/RECIST 1.1	Bone Scan (PCWG2)	Overall
CR	No Metastases (NE)	CR
CR,PR	SD	PR
SD	SD	SD
PD	SD	PD
SD	PD	PD

10.2 Myriad CCP Correlative studies.

These studies are already FDA-approved, standard-of-care studies, and will not be required for participation on this clinical trial. For those patients consenting to these

correlative studies, existing banked biopsy tissues from the original prostate specimens will be used for the Myriad CCP testing. Procedures for testing these tissues will be per existing clinical protocols.

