- Time to first SRE (defined as time to EBRT, time to first pathological bone fracture, time to spinal cord compression and time to surgical intervention) was statistically significantly longer in the Radium-223 chloride group compared to placebo (median number of months=15.6 for Radium-223 chloride versus 9.8 months for placebo (HR=0.658, 95 CI 0.522–0.830, p= 0.00037).
- Time to total ALP progression (defined as $\geq 25\%$ increase compared to baseline/nadir) was statistically significantly longer in the Radium-223 chloride group 7.4 months compared to placebo 3.8 months (HR = 0.167, 95% CI 0.129 – 0.217; p= <0.00001).
- Time to PSA progression (defined as a $\geq 25\%$ increase and an increase in absolute value of ≥ 2 ng/mL compared to baseline/nadir) was also significantly prolonged in patients receiving Radium Ra-223 dichloride compared to patients receiving placebo (HR = 0.643, 95% CI 0.539,0.768; p = <0.00001)
- A total ALP response (defined as a confirmed $\geq 30\%$ or $\geq 50\%$ reduction compared to baseline) at week 12 was observed in higher proportions of subjects who were treated with Radium-223 chloride group (47% and 3% respectively) compared to those in the placebo (3% and <1% respectively) group.
- Subgroup survival analysis showed a consistent survival benefit for treatment with Radium Ra-223 dichloride, independent of total alkaline phosphatase (ALP), current use of bisphosphonates, prior use of docetaxel and baseline ECOG status. The results from the phase III ALSYMPCA study regarding time to external beam radiation therapy (EBRT) for pain relief and fewer patients reporting bone pain as

an adverse event in the Radium Ra-223 dichloride group indicate a positive effect on bone pain.

The most common adverse reactions ($\geq 10\%$) in patients receiving Radium Ra-223 dichloride were nausea, diarrhea, vomiting, and peripheral edema (Table 2.1). Grade 3 and 4 adverse events were reported among 57% of Radium Ra-223 dichloride-treated patients and 63% of placebo treated patients. The most common hematologic laboratory abnormalities in Radium Ra-223 dichloride-treated patients ($\geq 10\%$) were anemia, lymphocytopenia, leukopenia, thrombocytopenia, and neutropenia (Table 2.2). Treatment discontinuations due to adverse events occurred in 17% of patients who received Radium Ra-223 dichloride and 21% of patients who received placebo.

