8.1 Dose Modifications

8.1.1 Dose Modification

Every effort should be made to administer the full dosing regimen of Radium Ra-223 dichloride. Adjustment of dose level is not permitted.

Study visits for administration of Radium-223 during the treatment period should occur at 28 day intervals (within a window of 0 and +14 days). Radium-223 cannot be administered earlier than 28 days from the previous administration. Dosing delays may be instituted under the following circumstances:

Disease progression:

The Investigator should delay cytotoxic chemotherapy, other systemic radioisotope, hemibody external radiotherapy or other investigational drug until the follow-up period. If such treatments have to be given during the treatment period, further study drug administrations must be discontinued.

Patients with a single PSA result that meets biochemical progression criteria may continue on treatment, at the investigator's discretion, until a confirmatory PSA result is returned. Upon confirmed biochemical progression study treatment MUST be discontinued.

Patients who demonstrate radiographic or clinical progression must discontinue study treatment.

Myelosuppression:

Treatment-related changes in hematology parameters may occur.

- If a patient experiences CTCAE v4.03 Grade 3 or 4 neutropenia, thrombocytopenia, or anemia the administration of study drug should be delayed until recovery to Grade 2 or better.
- If a patient experiences CTCAE v4.03 Grade 3 or 4 neutropenia, thrombocytopenia, or anemia lasting > 14 days, further study drug administrations must be discontinued.
- Blood transfusion is acceptable between study drug administrations but not prior to the start of the study. Use of biologic response modifiers, such as G-CSF or GM-CSF, is allowed in the management of acute toxicity.

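### For men with baseline PSA above 20, a 10% margin over the PSA nadir will record a stable PSA as confirmed progression fairly often if within-man variation is about 5% or more, even after the repeat test

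*Combined protocol and SAP*

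**What the plan says.** Section 10.1 assesses progression once EBRT and Cycle 2 are complete, so the Cycle 3 PSA is the first that can count. It sorts men by baseline PSA:

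- Baseline above 20, no fall: progression is 10% over baseline.
- Baseline above 20, some fall: "biochemical progression will be defined as a PSA rise greater than 10% of the PSA nadir". The same words are used whether the nadir is above or below 20.
- Baseline below 20: PSA must exceed 20 ng/mL as well as rise by 10%.

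A qualifying value must be validated "with a repeat PSA test no sooner than 5 days and no later than 14 days" after notification of the first result. No reason is given for the 10%, and no figure for PSA variability appears anywhere.

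The only other PSA progression definition in the document is in section 3.1.4, describing the phase III radium trial. It needs a rise of at least 25% together with "an increase in absolute value of ≥ 2 ng/mL compared to baseline/nadir".

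The definition has several uses. Section 8.1.1 states: "Upon confirmed biochemical progression study treatment MUST be discontinued". Section 7.4 also stops treatment for progression as section 10 defines it. The Study Summary lists PFS as a secondary objective. Section 11 asks whether the CCP assay "correlates with biochemical or clinical progression free survival in the study population", and section 1.3.2 asks the same of the HRD assay. In section 10.1, new bone lesions alone count as radiographic progression only if the biochemical definition is also met. The primary endpoint is the start of ADT or other systemic therapy, not progression itself.

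**The concern.** The minimum of several noisy measurements lies below the true level, and it falls further as readings accumulate. A margin of 10% over that minimum is therefore less than 10% over the man's true PSA. A later value at or slightly above his true level can qualify, and so can the repeat, because both are compared with the same low reference.

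If this happens often, stable men are recorded as progressors. PFS is shortened, and the biochemical PFS used for the CCP and HRD correlations gains events that are only noise. The bone-lesion branch becomes easier to meet, and study treatment ends. A stop at Cycle 3 can also leave a man short of the evaluability requirement in section 10. The trial has one arm, so no concurrent control carries the same error.

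**Working it through.** **The plan's own figure.** "The null hypothesis is that 99% of subjects will start systemic therapy within 15 months" and "The alternative hypothesis is that 80% of subjects will start systemic therapy within 15 months", so the free-of-therapy rates are 1% and 20%. With N = 20 and rejection at 2 or more,

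P(X ≥ 2) = 1 − (1−p)^20 − 20p(1−p)^19.

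- p = 0.01: 0.0169 (attained one-sided alpha).
- p = 0.20: 1 − 0.0115 − 0.0576 = 0.931. The stated 93% power reproduces.

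The plan gives no figure for how often its PSA rule misclassifies a stable man.

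**Why the margin shrinks.** Assume a CV of 5%. The expected minimum of 3 normal readings is 0.85 SD below the mean, so the nadir is about 0.85 × 5% = 4.2% low. The threshold is then 1.10 × 0.958 = 1.054 times the true level. With 10 readings the expected minimum is 1.54 SD below, or 7.7% low, and the threshold is 1.10 × 0.923 = 1.015 times the true level. By then the nominal 10% margin is about 1.5%.

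**Simulation.**
- *From the documents:* the 10% rule, one confirming repeat, assessment from Cycle 3, and the study calendar. This gives 4 looks (C3–C6), 5 with end of treatment, and about 8 by month 15 with three 3-monthly visits.
- *Assumed:* truly flat PSA; independent lognormal noise; CV of 3% to 10%; the nadir is the lowest of baseline, the EBRT and C2 values, and all later values so far.
- *Event:* a value and its repeat both above the threshold. 200,000 men per setting.

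Chance of at least one confirmed false progression:

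| Rule | CV 3% | CV 5% | CV 7.5% | CV 10% |
|---|---|---|---|---|
| 10% over nadir, C3–C6 (4 looks) | 3% | 28–29% | 58–60% | 73–75% |
| 10% over nadir, to month 15 (8 looks) | 6% | 52–54% | 83–87% | 93–95% |
| 10% over a fixed baseline, 8 looks | 1% | 12% | 27% | 37% |
| 25% and 2 ng/mL over nadir (section 3.1.4), 8 looks | 0% | 0.2% | 10% | 35–36% |

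In the 10% nadir rows, the lower figure leaves repeat values out of the nadir and the upper figure lets them update it.

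**What drives it.**
- *The running minimum.* At CV 5%, moving from a fixed baseline to the nadir raises the rate from 12% to 54%.
- *The repeat test helps.* Without it, the 8-look figures are 31% at CV 3% and 86% at CV 5%; with it, 6% and 54%. If the first and repeat values correlate at 0.5, they are 13% and 67%.
- *The absolute floor matters only at low PSA.* With a nadir above 20, a 10% rise already exceeds 2 ng/mL. At true PSA 25 and CV 5%, adding a 2 ng/mL floor to the 10% rule leaves 54% unchanged. At true PSA 10 it cuts 54% to 0.5%, and at PSA 2 to 0%.
- *The no-fall branch rarely applies.* With flat noisy PSA, baseline is the lowest of 11 readings for only 1 man in 11, so by the tenth later test 10 of 11 men are under the nadir rule.

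**Effect on the primary test, if false calls lead to ADT.** Suppose 20% of men have baseline above 20, and half of those who would otherwise be successes start ADT after a false call. The free rate becomes 0.20 × (1 − 0.20 × 0.50) = 0.18, and power is 1 − 0.0189 − 0.0829 = 0.898. At an extreme of 40% and 90%, the free rate is 0.20 × (1 − 0.36) = 0.128 and power is 74.6%.

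**The case against.** Several counter-arguments are sound and limit the point.

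- **The CV is assumed.** A reader might infer that ordinary PSA variation is shown to make many stable men progressors. The documents do not support that: the 8-look result runs from 6% to 95% with a CV they do not supply. At about 3% or less the problem is small.
- **The affected group may be small.** Men with baseline below 20 have an absolute threshold and are untouched. The only PSA level given for a similar cohort, in section 2, is a median of 5.4.
- **The scenario is severe.** Eligible men enter with rising PSA, yet the model holds it flat to month 15. Follow-up windows are wide (+90/−30 days). With six looks, CV 5% gives 42%.
- **The repeat does protect to a degree**, most clearly at low CV.
- **The primary endpoint is one step removed.** A reader might infer that the primary result is biased. Sections 1.1.1 and 11 do link ADT to progression, but the counted event is the start of therapy, and nothing in the documents requires ADT on biochemical progression.
- **The other uses are secondary or exploratory.** PFS has no analysis in section 11, and the CCP and HRD work is optional.
- **The section 3.1.4 margin is no general replacement.** It comes from castration-resistant disease. Applied to men below 20 it would date progression much earlier: from PSA 5 with an assumed 12-month doubling time, a rise to 7 takes 12 × log2(1.4) = 5.8 months, whereas reaching 20 takes 12 × log2(4) = 24 months.

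All of this stands. None of it changes how the rule behaves in men with baseline above 20 once the CV reaches about 5%.

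**Conclusion.** The point holds for men with baseline PSA above 20. Applied exactly as written, the rule gives a man with flat PSA about a 6%, 52–54%, 83–87% or 93–95% chance of confirmed false progression over 8 looks at CVs of 3%, 5%, 7.5% and 10%. The main cause is a 10% margin over a running minimum. The absent absolute floor adds to it only when the nadir is below 20, where the text repeats the above-20 branch and so makes no distinction.

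The consequences are direct for PFS, for exploratory biochemical PFS, for the new-bone-lesion branch and for continuation of study treatment. For the primary test they are conditional: the illustration takes power from 93% to about 90%, and larger losses need both a large share of men above 20 and nearly universal ADT after false calls. The size rests on the assumed CV, flat true PSA, about 8 on-time looks and an unstated share of men above 20.

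**What to change.** In section 11, for men with baseline PSA above 20 only, pre-specify a second derivation of PFS and biochemical PFS. It would use the section 3.1.4 margin (at least 25% and at least 2 ng/mL over baseline or nadir), confirmed by the existing repeat test, and count any earlier start of systemic therapy as an event. Report it beside the 10% rule, and do not rest the PFS or CCP/HRD conclusions on the 10% rule alone. Leave the definition for men below 20 unchanged.

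The sponsor should also reconcile two matters in the text: the two nadir branches in section 10.1 with identical wording, and the use of section 10.1 both as an endpoint and, through sections 7.4 and 8.1.1, as the trigger for ending treatment. No stopping rule is proposed here.

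The cost is a short addition to section 11 and one further derivation from PSA values already collected. There are limits. True progression is dated somewhat later in this derivation, and false calls remain at a CV of 10% or more (about 35%). It cannot undo treatment stops or ADT starts that the 10% rule has already triggered.
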